[name] [name]. Tasks: carrying out interventions, data collection, participation in the production of publications and presentations.

[name] [name]. Tasks: carrying out interventions, data collection.

[name] [name]. Tasks: assessment and design of respiratory tests, participation in publications and presentations.

[name] [name]. Tasks: assessment and design of respiratory tests, participation in publications and presentations.

[name] [name]. Tasks: participation in the design of the work, data collection and participation in the production of publications and presentations.

WORK PLAN

1. Patient recruitment and study of patients: January 2015 to December 2017.

2. Collection of data to complement the Clinical History.

Step 3. Introduction to the study. Explanation of the procedure. Signed consent form.

Step 4. Measurement of parameters:

1. Measurement of pain, Mc Gill test.
2. Measurement of respiratory parameters. Spirometry.
3. Quality of Life Measure. SF-36.
4. Measured with the Minnesota Multiphasic Personality Inventory.
5. Counting days of treatment.

Step 5. Start of the respiratory physiotherapy programme. It will be carried out in the respiratory physiotherapy unit of the University Hospital of Gran Canaria [name]. Patients will be divided into the two groups described above and will be included in the treatment programme. The sequence for the intervention group will be as follows:

1. Explanation of the programme.
2. Placement of external analgesic measures (TENS). The frequency of application would be 100 hz as this is the type of application that produces the greatest analgesia.
10,11,12,13
3. Implementation of the treatment regimen, for x days.
4. In the middle of the programme, measurement of all the above

parameters. Step 6. Continuation of the physiotherapy programme.

Step 7. Completion of the physiotherapy programme. Measurement of all parameters again, plus accounting of treatment days.

In the control group, the same would be done but no intensity would be given when applying TENS. The steps to follow would be the same.

ECONOMIC STUDY

Within the economic study that will define this work, we will highlight two fundamental points:

Portable spirometer brand..... 1500 Euros.

Publication of results..... 1500 Euros.

Attendance at Conferences and Scientific Conferences 750 Euros.

Publication in scientific journals in the sector..... 750 Euros.

TOTAL 3000 Euros.

BIBLIOGRAPHY

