Acute postoperative pain is pain that occurs when a patient undergoes surgery, either associated with the surgical procedure and the pre-existing disease or a combination of both (1).

For proper postoperative pain control, effective and safe analgesic management during the perioperative period (preoperative, intraoperative and postoperative) should be carried out, as well as to avoid future sequelae. Specifically, this involves:

1. Minimise the incidence and severity of acute perioperative pain.
2. Educate patients and their families about the importance of their involvement in effective pain management.
3. Improving patient wellbeing.
4. To reduce postoperative complications secondary to pain management and, as far as possible, the length of hospital stay (1).

CONTEXTUALISATION OF PAIN

Pain following thoracic surgery has a number of particular characteristics:

- It is considered the most severe acute postoperative pain.
- The inadequate control of pain favours the occurrence of serious postoperative complications such as atelectasis and respiratory infections.
- Adequate relief allows for intensive physiotherapy, reducing the occurrence of such complications.
- Functional residual capacity (FRC) decreases (6).

Several mechanisms are involved in the aetiopathogenesis of this pain, including the following:

- Surgical incision.
- Lung resection.
- Pleural drainage tubes.
- Inflammation.
- Injury to intercostal nerve or costal spinal roots (6)

Potential problems may also arise, such as limitation of movement in the upper limbs and rib cage, muscle shortening (derived from the surgical act itself) and the consequent reduction in joint range (7).

PAIN AND PHYSIOTHERAPY

In accordance with the concept of Science, defined by the Royal Academy of the Spanish Language as "*a methodically formed and ordered body of doctrine that constitutes a particular branch of human knowledge*", *in order to describe, interpret and analyse how Physiotherapy as a Science approaches pain, it is necessary to describe and deepen the concept of pain from the point of view of Physiotherapy.*³ In order to describe, interpret and analyse how Physiotherapy as a Science approaches pain, it is necessary to describe and analyse the concept of pain from the point of view of Physiotherapy.

There are three types of pain from a physiotherapy point of view:

- a. Pain of biochemical origin.
- b. Pain of neuralgic origin.
- c. Pain of mechanical origin.

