Thoracic surgery has a high incidence of complications. The most frequent are atelectasis and respiratory infections, especially pneumonia. Other complications also include arrhythmias, hypotension and shock, myocardial infarction, pulmonary oedema and embolism, respiratory failure, prolonged air leaks and dehiscence, among others (26).

The principles which, in principle, apply are:

1. To achieve effective analgesia in order to be able to perform efficient respiratory physiotherapy. Physiotherapy manoeuvres should always be started after the absence of pain has been achieved.
2. Oxygen therapy, to prevent hypoxaemia.
3. Humidification and aerosol treatment. Its main purpose is to fluidise sputum, humidify the airway, mobilise secretions and administer drugs by inhalation.
4. Pharmacological treatment, in order to clear secretions, increase airway calibre or support the cilia expulsion mechanism.
5. Respiratory physiotherapy, with manoeuvres aimed at promoting thoracic expansion and the elimination of secretions. The following manoeuvres are basic:
 - a. Diaphragmatic mobilisation.
 - b. Hyperinflation or thoracic expansion therapy.
 - c. Postural drainage.

The primary goal of respiratory rehabilitation after chest surgery is to bring the patient to maximum physical potential, as well as to reduce symptoms and pathophysiological consequences of respiratory impairment (23).

Respiratory physiotherapy is essential to achieve thoracic expansion and diaphragmatic mobilisation, avoid diaphragmatic dysfunction and reduce the occurrence of atelectasis and respiratory infections. It should be accompanied by intense analgesia with as few side effects as possible.

The aim of this study focuses on the need, through physiotherapeutic means, to achieve the highest possible level of analgesia for these patients without generating morbidity.

JUSTIFICATION

One of the fundamental bases of physiotherapy is the intervention in pain control. Post-surgical pain in thoracic surgery is considered to be one of the most intense pains that exist. Based on this principle, the aim of this work is to demonstrate that pain control, recovery, readaptation and development of respiratory parameters are normalised with greater precision and in less time.

OBJECTIVE

The objective of the present study, in accordance with the hypothesis determined, will be to demonstrate four points relating to the activity of physiotherapy. These points will be the following:

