The different respiratory parameters will be measured by spirometry (Siebel spirometer): Forced Vital Capacity (FVC); Forced Expiratory Volume of the first second (FEV₁); FEV₁/FVC (Tiffeneau Index).

COST ANALYSIS

Activity times shall be measured in two groups of patients. In all cases, the recovery time and return to normal life will be established. A study of the costs of visits and physiotherapy treatment of these patients until their return to normality prior to the intervention will be carried out.

STATISTICAL STUDY

Data collection will be carried out over a period of three years. There are no reliable data to allow statistical calculation of the sample size, but it is estimated that 30 patients are needed for each of the subgroups described, giving a total sample size of 180 patients.

This is a prospective, randomised, longitudinal study.

STATISTICAL ANALYSIS

Quantitative variables will be described by means of centralisation and dispersion indices: mean, standard deviation and range. The hypothesis of normality of the variables will be verified using the Kolmogorov-Smirnov test for a single sample. Qualitative variables will be treated by analysing the absolute frequency of occurrence of each of the categories, as well as the relative frequencies. Categorical data will be compared using the χ^2 test or Fisher's exact test when necessary. RANOVA will be used when more than 2 means of related variables are to be compared. Student's t-test should be used when comparing 2 related or independent means. In addition, multivariate analysis (multiple linear and logistic regression) will be used for the correct modelling of the relationship between variables. The accepted level of statistical significance is $p<0,05$. Data will be analysed using the statistical package SPSS version 15.0 (SPSS, Inc, Chicago).

REQUEST FOR EVALUATION BY THE CENTRE'S ETHICS COMMITTEE

Immediate application shall be made to the Centre's Research Ethics Committee.

APPLICABILITY OF THE RESULTS

The applicability of the results will be carried out in the Rehabilitation Services that have a Respiratory Physiotherapy unit.

From an economic point of view.

1. The TENS analgesia technique is a low-cost technique and, according to the existing literature, it is effective in the process under study.

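### The final pain, spirometry and SF-36 measurement is tied to completing a programme of open length, with no fixed date and no provision for patients who leave early, so final values may be missing selectively by arm and taken at different times

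*Protocol*

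**What the plan says.** The Work plan in the protocol gives three measurement points.

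- **Step 4, before treatment:** McGill, spirometry and SF-36, with a personality inventory and a count of treatment days.
- **Step 5, midpoint:** "In the middle of the programme, measurement of all the above" parameters. The length of the programme is a placeholder: "Implementation of the treatment regimen, for x days".
- **Step 7, end:** "Completion of the physiotherapy programme. Measurement of all parameters again", together with a count of treatment days.

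Controls follow the same schedule: "The steps to follow would be the same". No section gives the final assessment a date, and none says what is collected from a patient who stops physiotherapy early or is admitted to hospital after randomisation. Hospital admission for complications appears only among the exclusion criteria.

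One sentence, under Cost analysis, does reach every patient: "In all cases, the recovery time and return to normal life will be established". It concerns recovery time and resumption of normal life, not pain, lung function or quality of life.

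**The concern.** An assessment triggered by an event is taken only in patients who reach the event. Someone who gives up physiotherapy because it hurts, or is readmitted, does not reach Step 7, and the schedule calls for no substitute.

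The protocol's own rationale gives a reason why this loss might depend on treatment. Under Contextualisation of pain it says "The inadequate control of pain favours the occurrence of serious postoperative complications such as atelectasis and respiratory infections", and TENS is there to control pain. If TENS works, more controls who are doing badly could leave. The remaining controls would then look better than the randomised control group, and part of the benefit would be hidden. If instead more TENS patients who are doing badly leave, the benefit would be overstated.

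A second effect needs no one to leave. Objective three predicts less time in outpatient care with TENS. If that is right, Step 7 comes earlier in one arm. The background on respiratory mechanics says lung volumes take 1 to 2 weeks to return to preoperative values, so time since surgery could itself move the spirometry.

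This belongs in the protocol. An analysis plan can choose analysis sets and missing-data methods, but it cannot supply visits that were never scheduled.

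**Working it through.** **1. The plan's own figure.** 30 patients × 2 arms × 3 surgical groups = 180, as stated under Statistical study. Pooled over surgical groups, that is 3 × 30 = 90 per arm. The protocol gives no effect size, SD, power, dropout rate or readmission rate, so everything below is illustration under stated assumptions.

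**2. What each type of patient yields if the schedule is followed literally.**

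| Patient | Baseline | Midpoint | Final |
|---|---|---|---|
| Completes physiotherapy | yes | yes | yes |
| Stops TENS only, completes physiotherapy | yes | yes | yes |
| Leaves physiotherapy after the midpoint | yes | yes | none scheduled |
| Leaves physiotherapy before the midpoint | yes | none scheduled | none scheduled |

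**3. Bias formula.** Let a proportion p of an arm leave, and let leavers be d SD worse than completers (higher = worse). Then

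completer mean = full-arm mean − p × d,

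so the TENS-minus-control difference among completers is off by

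bias = (p_control − p_TENS) × d.

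**4. Numbers (leaving proportions and d are assumed).**

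- Equal leaving, same d: bias = 0.
- 15% v 5%, d = 0.5: 0.10 × 0.5 = 0.05 SD.
- 15% v 5%, d = 1: 0.10 × 1 = 0.10 SD.
- 20% v 5%, d = 1: 0.15 × 1 = 0.15 SD.

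The sign depends on which arm loses more patients.

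**5. Relative to sampling error.** With 15% and 5% lost, completers number 90 × 0.85 = 76.5 and 90 × 0.95 = 85.5.

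SE = √(1/76.5 + 1/85.5) = 0.157 SD.

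0.05/0.157 = 0.32 and 0.10/0.157 = 0.64. Using the full 90 per arm (SE = √(2/90) = 0.149) would overstate the second ratio slightly, at 0.67.

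**6. Loss of precision, which occurs even if leaving is balanced.** With 90 v 90 and two-sided 5%, the effect detectable with 80% power is (1.960 + 0.842) × √(2/90) = 0.418 SD. Assumed losses of 5%, 10%, 20% and 30% leave 171, 162, 144 and 126 completers, and power for that effect falls to 78%, 76%, 71% and 65%.

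**7. Timing among completers.** The programme length is not stated, so the difference in timing between arms cannot be quantified.

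**The case against.** The strongest reply is that the Work plan is a short account of the normal course. It is silent on early leavers; it does not forbid measuring them. Several stronger readings that a reader might infer do go beyond the text.

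- **That leavers are never measured again.** All parameters are also taken at the midpoint in both arms, so a later leaver has a full post-baseline set.
- **That stopping TENS means losing the final measurement.** Step 7 depends on finishing physiotherapy. A patient who declines TENS but continues the sessions is measured, and the intensity is already limited to what the patient can bear.
- **That the analysis is of completers only.** No analysis set is stated. It may be in an analysis plan not shown, so its absence here is not a fault. The protocol does name RANOVA, which in its classical form needs a value at every time point, but that does not fix the analysis set.
- **That complications will drive heavy loss.** The statement "Thoracic surgery has a high incidence of complications" is background on thoracic surgery in general. These patients start after 7 days, free of complications and drains, and no rate of readmission or stopping is given for them.

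What remains is the collection gap. No final value is scheduled for a patient who leaves physiotherapy, and no date stands in for completion. The Cost analysis sentence about all cases does not cover the three outcomes at issue. The midpoint value helps, but it is not the final value, and those who leave before it have only baseline.

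**Conclusion.** The point holds as a gap in data collection. Because the last measurement depends on completing a programme of unstated length, final pain, spirometry and SF-36 values may be missing selectively by arm, and may be taken at different times after surgery even among completers.

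Its importance is uncertain. The bias is nil if leaving is equal with the same d in both arms, and 0.05 to 0.10 SD (about 0.3 to 0.64 of a standard error) under an assumed 10-point gap with d of 0.5 to 1, pooling the surgical groups. The documents support neither a particular rate nor a direction. It would be too strong to conclude that the randomised comparison is lost. The case for change is that the remedy costs little and cannot be applied after the data are in.

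**What to change.** State in the Work plan one final assessment time counted from randomisation, identical in both arms, and take McGill, spirometry and SF-36 then for every randomised patient, whether or not TENS or physiotherapy has been stopped. The time has to be named outright: while the length is a placeholder, it cannot be derived from when Step 7 would have occurred.

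Record stopping TENS, stopping physiotherapy and withdrawing consent as separate events, each with its reason and date. Only withdrawal of consent should end data collection. Allow the questionnaires by telephone or post when a patient cannot attend.

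The end-of-programme measurement and the count of treatment days can stay as they are; they serve the cost objective. No treatment rule changes.

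**Cost:** protocol wording and one assessment at a set date, which for some patients will not coincide with the last session. Some spirometry will still be missing, because it needs attendance.

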Annex 1. Quality of Life Questionnaire SF-36

Tabla 1. Contenido de las escalas de SF-36			
Dimensión	N.º de ítems	Pior puntuación	Mejor puntuación
Función física	10	Muy limitado para realizar cualquier actividad física, incluido bañarse o ducharse (origen físico)	Puede realizar todo tipo de actividades físicas, incluidas las más vigorosas, sin limitaciones
Rol físico	4	Problemas con el trabajo u otras actividades diarias (origen físico)	Ausencia de problemas con el trabajo u otras actividades físicas diarias (origen físico)
Dolor corporal	2	Dolor muy intenso y extremadamente limitante	Ningún dolor. Sin repercusión
Salud general	5	Considera mala la propia salud y cree imposible que empeore	Considera su propia salud como excelente
Vitalidad	4	Se siente cansado y exhausto continuamente	Se siente muy dinámico y energético continuamente
Función social	2	Su salud física o emocional no le permite, con gran frecuencia, relacionarse socialmente	Su salud física o emocional le permite relacionarse socialmente de un modo normal
Rol emocional	3	Problemas con el trabajo u otras actividades diarias (origen emocional)	Ausencia de problemas con el trabajo u otras actividades físicas diarias (origen emocional).
Salud mental	5	Sentimiento de angustia y depresión continuamente	Sentimiento de felicidad, tranquilidad y calma continuamente
Ítem de transición de salud	1	Considera su salud mucho peor ahora que hace 1 año	Considera su salud general mucho mejor ahora que hace 1 año
Total 8	36	0	100

1. Overall, you would say that your **health** is: 1 Excellent

2 Very good 3

Good

4 Regular

5 Mala

2. How would you say your **health is now compared to a year ago?** 1
Much better now than a year ago

2 Slightly better now than a year ago 3

About the same as a year ago 4 Slightly

worse now than a year ago

5 Much worse now than a year ago

THE FOLLOWING QUESTIONS REFER TO ACTIVITIES OR THINGS THAT YOU MIGHT DO ON A NORMAL DAY.

3. Does your current health limit you from making **strenuous efforts**, such as running, lifting heavy objects, or participating in strenuous sports? 1 Yes, it limits me a great deal.

2 Yes, it limits me a little

bit 3 No, it does not limit

me at all

4. Does your current health limit you to **moderate exertion**, such as moving a table, vacuuming, bowling, or walking for more than an hour? 1 Yes, it limits me a lot.

2 Yes, it limits me a little

bit 3 No, it does not limit

me at all

5. Does your current health limit your ability to **pick up or carry your shopping bag**?
1 Yes, it limits me a lot 2

Yes, it limits me

somewhat

3 No, it does not limit me at all

6. Does your current health limit your ability to **climb several flights of stairs**? 1 Yes, it limits me a lot.

2 Yes, it limits me a little

bit 3 No, it does not limit

me at all

7. Does your current health limit your ability to **climb a single flight of stairs**? 1 Yes, it limits me a lot.

2 Yes, it limits me a little

bit 3 No, it does not limit

me at all

8. Does your current health limit you from **bending or kneeling**?
1 Yes, it limits me a lot 2

Yes, it limits me

somewhat

3 No, it does not limit me at all

9. Does your current health limit you to walk **a kilometre or more**? 1 Yes, it limits me a lot

2 Yes, it limits me a bit 3

No, it does not limit me at

all

10. Does your current health limit you to walk **several blocks** (several hundred metres)? 1
Yes, it limits me a lot

2 Yes, it limits me a bit 3

No, it does not limit me at

all

11. Does your current health limit you to walk **only one block** (about 100 metres)? 1 Yes, it limits me a lot

2 Yes, it limits me a bit 3

No, it does not limit me at

all

12. Does your current health limit your ability to **bathe or dress yourself?**

1 Yes, it limits me a lot 2

Yes, it limits me

somewhat

3 No, it does not limit me at all

THE FOLLOWING QUESTIONS REFER TO PROBLEMS IN YOUR WORK OR DAILY ACTIVITIES.

13. During the last 4 weeks, did you have to **reduce the time you** spent at work or on your daily activities because of your physical health? 1
1 Yes

2 No

14. During the last 4 weeks, did you do **less** than you would have liked to do, because of your physical health? 1 Yes
1 Yes

2 No

15. During the last 4 weeks, did you have to **give up any tasks** at work or in your daily activities because of your physical health? 1 Yes

2 No

16. During the last 4 weeks, did you have **difficulty** in doing your work or daily activities (e.g., did it cost you more than usual), because of your physical health?

1 Yes

2 No

17. During the last 4 weeks, did you have to **reduce the time you** spent at work or in your daily activities because of an emotional problem?

(like being sad, depressed, or nervous?)

1 Yes

2 No

18. During the last 4 weeks, did you do **less** than you would have liked to do, because of any emotional problems (such as being sad, depressed, or nervous)?

1 Yes

2 No

19. During the last 4 weeks, did you not do your work or daily activities as **carefully** as usual, because of some problem

emotional (such as being sad, depressed, or nervous?)

1 Yes

2 No

20.- During the last 4 weeks, to what extent have your physical health or emotional problems hindered your usual social activities with family, friends, neighbours or other people?

Not at all

A little

Regular

Quite a lot

Very much

21. 21.- Did you have **pain** in any part of your body during the last 4 weeks?

1 No, not at all 2

Yes, very little 3

Yes, a little bit

4 Yes, moderate 5

Yes, very much

6 Yes, very much so

22. During the last 4 weeks, to what extent has the pain made it difficult for you to do your usual work (including work outside the home and housework)?

1 Nothing

2 Somewhat

3 Regular

4 Quite

5 A lot

THE FOLLOWING QUESTIONS ARE ABOUT HOW YOU HAVE BEEN FEELING AND HOW THINGS HAVE BEEN GOING FOR YOU OVER THE LAST 4 WEEKS. FOR EACH QUESTION, PLEASE ANSWER THE QUESTION THAT MOST CLOSELY RESEMBLES HOW YOU HAVE BEEN FEELING.

23. During the last 4 weeks, how much of the time did you feel full of **vitality**?

1 Always

2 Almost always 3

Often 4 Sometimes

5 Only ever 6

Never

24. 23.- During the last 4 weeks, how much time were you very **nervous**?

1 Always

2 Almost always 3

Many times 4

Sometimes

5 Only ever 6 Never

25. During the last 4 weeks, for how long did you feel so **low in morale** that nothing could cheer you up?

1 Always

2 Almost always 3

Often 4 Sometimes

5 Only some of the time

6 Never

26. During the last 4 weeks, how much of the time did you feel **calm and peaceful**? 1 Always

2 Almost always 3

Often 4 Sometimes

5 Only ever 6 Never

27. During the last 4 weeks, how much of the time did you have a **lot of energy**? 1 Always

2 Almost always 3

Often 4 Sometimes

5 Only ever 6 Never

28. During the last 4 weeks, how much of the time did you feel **discouraged and sad**? 1 Always

2 Almost always 3

Often 4 Sometimes

5 Only ever 6 Never

29. During the last 4 weeks, for how long have you felt **exhausted**? 1 Always

2 Almost always 3

Often 4 Sometimes

5 Only ever 6 Never

30. During the last 4 weeks, how long did you feel **happy**? 1 Always

2 Almost always 3

Often 4 Sometimes

5 Only some of the time

6 Never

31. During the last 4 weeks, for how long did you feel **tired**? 1 Always

2 Almost always 3

Often 4 Sometimes

5 Only ever 6 Never

32. During the last 4 weeks, how often has physical health or emotional problems made it difficult for you to carry out social activities (such as visiting

friends or family)?

1 Always

2 Almost always 3

Sometimes

4 Only ever 5 Never

PLEASE SAY WHETHER YOU THINK EACH OF THE FOLLOWING STATEMENTS IS TRUE OR FALSE.

33. I think I get sick more easily than other people. 1 Absolutely true

2 Fairly certain 3

Don't know

4 Quite false

5 Completely false

34. I am as healthy as anyone else.

1 Absolutely true 2

Quite true

3 I don't know

4 Quite false

5 Completely false

35. I think my health is going to get worse.

1 Absolutely true 2

Quite true

3 I don't know

4 Quite false

5 Completely false

36. My health is excellent.
1 Absolutely true 2

Quite true

3 I don't know

4 Quite false

5 Completely false

